2.0 OBJECTIVES AND SCIENTIFIC AIMS

1. The primary objective is to determine the feasibility of using the visual picture naming task in pediatric patients in the clinical setting. Feasibility will be defined as being able to accrue an average of 2 patients a week who successfully name and recognize sufficient numbers of pictures so that the thresholds for sedation and memory can be determined in each individual (as described in Section 11.0, Aim 1).
2. The strength of propofol amnesia (the effect of propofol on memory not related to sedation) will be estimated as a difference between thresholds for amnesia (loss of memory) and sedation (loss of verbal responsiveness)

MEMORIAL SLOAN-KETTERING CANCER CENTER IRB PROTOCOL

IRB#: 12-006A(5)

Hypothesis 1: The threshold effect for memory will occur significantly sooner, i.e. at lower drug concentrations, than the threshold effect for sedation, as illustrated in Fig 2 (the threshold for memory effect is illustrated by the light gray curves in the Figures, and for sedation by the dark curves).

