The methods used to assess the amnesic properties of drugs in the clinical setting are quite limited in comparison to controlled research settings. (22) Frequently measures of memory are used which cannot differentiate among the various factors that impair memory in the clinical setting. For example, anxiety in the peri-operative setting can itself impair memory for events before the administration of anesthesia. (23) Other difficulties in translation of methods to the clinical setting include the use of other drugs, timing of measurements, the presence of painful treatments, etc. (24) One of most difficult issues to address is the ability to separate the amnesic and sedative effects of drugs on memory. (25) (21) A behavioral paradigm that could separate sedative and amnesic effects of drugs easily applied in the clinical setting would allow the ability to measure the influence of the amnesic properties of a given drug on outcome, for example patient satisfaction with anesthesia or recall of procedure events. Over the past decade we have developed

MEMORIAL SLOAN-KETTERING CANCER CENTER IRB PROTOCOL

IRB#: 12-006A(5)

methods to measure amnesic versus sedative effects, in particular with propofol, in the research setting using volunteers. (7,16,21)

The drug ramping paradigm

A simple paradigm that allows amnesia to be differentiated from sedation is to infuse drug in increasing concentrations over a period of ~10 minutes. During this time period, as drug concentration and sedation are increasing, visual stimuli are presented. Importantly, these stimuli are attended to by performance of a task, in this case by naming a picture. A positive response on the task, naming the picture either correctly or incorrectly, confirms that the stimulus was processed sufficiently to be learned and allow testing for subsequent recognition.

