9.0 PRIMARY OUTCOMES

Several factors affect the feasibility of the proposed study design, including 1) accrual rate in the proposed 4 – 6 months study period, 2) drop-out rate (children who complete the picture naming task during infusion but fail to complete the memory task post recovery), and 3) sufficient data (e.g., few observations during the picture naming task because the child falls asleep quickly; few accurate responses during the memory task).

The accrual and dropout rates will be addressed by keeping a running tally of the number of recruited participants to monitor the recruitment numbers. Our target is to recruit at least an average of 2 out of the anticipated 4 – 6 children per week. However, it would be impractical to set a fixed recruitment target for a pilot study of this nature.

Factors associated with data sufficiency will have to be determined after the data have been collected. For example, we have to wait until the data have been collected before we can begin calculating the proposed threshold statistic (Section 14 below). The statistical computer packages may or may not be able to derive a stable estimate of the threshold measure per child. This will have to be determined after each child's data have been collected, entered, and fitted for the threshold statistics.

It is premature to anticipate a statistically reliable difference between the two threshold measures, one for the *sedative* effect threshold and the other for the *memory* effect threshold. These will have to be ascertained after the data have been collected, entered, fitted, and plotted in the manner similar to Figures 1 and 2 above. It is plausible that the threshold values are similar in some children and quite different in some other children. An important goal of this study is to examine the variability between the two threshold values among the sample of children.

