10.0 CRITERIA FOR REMOVAL FROM STUDY

If the patient cannot adequately perform the picture naming task (defined as verbally responding to >80% of the pictures presented before falling asleep, or half way through the list in the case of no sedation) through a significant portion of the initial 10 minute

MEMORIAL SLOAN-KETTERING CANCER CENTER IRB PROTOCOL

IRB#: 12-006A(5)

infusion, data collection will be stopped, the patient withdrawn from the study, and no further testing be performed. Similarly, if the patient is unable or unwilling to perform the recognition task, he/she will be withdrawn from the study. In the extremely unusual circumstance of severe or unanticipated toxicity from the administration of propofol (e.g. allergic reaction), the participant will be withdrawn from the study. Any participant who is removed from the study prior to the start of their procedure for reasons other than toxicity (i.e., inability or unwillingness to complete the practice or actual task) will then be administered propofol as per normal clinical practice for their procedure.

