Aim 2. Illustrative Examples. Aim 2 involves the calculation of a “sedation threshold” and a “memory threshold” for each child. Figures 1, and 2 provide illustrative examples on how the separate sedative and amnesic effects will be estimated statistically. An example is provided below to explain the procedures and the analytic plan.

1. “Sedation threshold”: During the 10-minute infusion of propofol, children will be presented with pictures at 5-second intervals and asked to name the picture. They will be asked to name each picture (e.g., cat, tree, pencil, etc.). A valid response is naming of the picture within 5 seconds, either correctly or incorrectly. The important response measure is whether the child is awake enough to perform the naming task. Though the picture list is a validated set of stimuli, as described in Section 7.0, some stimuli may end up being too difficult to name for children of this age group. Thus no response due to sedation may be confounded by no response due to an inappropriately difficult stimulus. Responses from the control group of children will be used to eliminate problematic stimuli which reach a given criterion of no response at both sites.

In Figures 1 and 2, the dark circles with a value of 1 on the y-axis represent that the participant is making valid responses. The dark circles with a value of 0 on the y-axis represent lack of a valid response because the participant is sedated to the point of impaired response performance as propofol concentration continues to increase. As the child gets sedated and becomes gradually sleepier as the infusion continues, he/she is less likely to make a valid response (thus the increased frequency of dark circles at the bottom of the Figures as image number increases). The dark line in Figure 1 represents the estimated sedative effects over time.

There is a vast literature in psychophysics on modeling the shapes of these curves. Since the seminal paper by Quick (1974; *Kybernetik*, 16: 65-67; PMID: 4453110), the model below has been used extensively in modeling various psychophysical functions. We will use an asymmetric Weibull cumulative density function $F(x)$ to model the overall probability of a valid response $G(x)$ over time x :

$$\begin{aligned} G(x) &= 0.5 + 0.5 \cdot F(x) \\ &= 0.5 + 0.5 \left[1 - e^{-(\alpha \cdot x)^\beta} \right], \end{aligned}$$

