where $\alpha > 0$ and $\beta > 0$ are the scale and shape parameters, respectively, and $x \geq 0$. (35) The constant of 0.5 assumes a 50-50 chance of a random response in a psychophysical task. Conventionally, the median of $F(x)$ is called the “threshold” of the underlying psychometric function (the value of x for which $F(x) = 0.5$). Because of the assumed 0.50 constant in $G(x)$, and the 0.5 times the median of the Weibull, the threshold estimate is the x value of an overall 75% response probability given the Weibull parameters. The threshold of a psychometric function generally represents the strength of stimulus that elicits a sensation or a noticeable difference. In this case the sedation threshold represents the time value of x when sedation is actuated. We will estimate one sedation curve and its corresponding threshold for each child.

MEMORIAL SLOAN-KETTERING CANCER CENTER IRB PROTOCOL

IRB#: 12-006A(5)

2. "Memory threshold": When the anesthesia has worn off at approximately 1 hour later, the child will be presented with another list of 120 pictures with half having been presented during the initial infusion of propofol. At the presentation of each picture, the child will be asked whether or not he/she remembers having seen it previously. Each response will be coded as correct (true positives and true negatives) or incorrect (false positives and false negatives). A curve may be fitted to the memory recognition data to estimate the average memory decay function for each child. In Figure 1 and 2 this is represented as the light gray curve, which can be modeled as $1 - G(x)$ above. Similarly, a threshold represents the time value (picture number) when memory fades below threshold.

The *sedation* threshold in Figure 1 is at image 25 (250 seconds), while the *memory* threshold is at approximately image 28 (280 seconds). This 30-second / 3 picture difference is taken to represent that sedation occurs concurrently with memory decay. Alternatively, in Figure 2, the *sedation* threshold is at image 58 (580 seconds) while the *memory* threshold is approximately at image 40 (400 seconds). This larger difference of 180 seconds / 18 pictures is a measure of how much sooner amnesia occurred in this instance than sedation. In this latter case, a measurable amnesic effect of 180 seconds can be inferred from the two threshold values.

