Calculations of the sedation and memory thresholds. The overall statistical paradigm will involve non-linear regression modeling to estimate $G(x)$ functions for the memory and sedation curves for each child in order to address the main hypothesis:

"The threshold effect for memory will occur significantly sooner, i.e. at lower drug concentrations, than the threshold effect for sedation".

Sample Size Considerations. The proposed pilot sample of 35 children accrued to the propofol group is primarily determined by our plan to complete the study within 4-6 months. In our experience we have a pool of approximately 10 children who undergo anesthesia for clinical scans each week who would meet the eligibility criteria. Among them an anticipated 50% would agree to participate in this study. If half of these (2-3/week) produce data of sufficient quality to be able to perform curve fitting as described above, we expect to complete recruitment within 5 months.

A sample of 35 children will also yield an 80% power in a one-sample t-test against the null that the difference in the sedation and memory thresholds is zero (null $\sim N(0, 1)$), assuming a two-sided Type-I error rate of 0.05, and an alternative population distribution with a mean of 0.50 and a standard deviation of 1.0. The statistical power was estimated by the G*Power computer program.

MEMORIAL SLOAN-KETTERING CANCER CENTER IRB PROTOCOL

IRB#: 12-006A(5)

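### Aim 2 fixes the same limits for the naming and recognition curves, so a zero threshold difference is not in general the value for no amnesia beyond sedation

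*Combined protocol and SAP*

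**What the plan says.** Section 2.0, Objective 2, measures the strength of propofol amnesia by the gap between the sedation and memory thresholds. Hypothesis 1 expects the memory threshold to come significantly sooner.

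Section 11.0, Aim 2, commits to G(x) = 0.5 + 0.5F(x), with F a Weibull distribution function whose scale and shape are the only free parameters. The reason given is "The constant of 0.5 assumes a 50-50 chance of a random response in a psychophysical task". The threshold is the x at which F = 0.5, that is, G = 0.75. The same section applies G to both curves of each child, although its wording for the recognition curve is permissive and offers 1 - G(x). The power statement rests on a "one-sample t-test against the null that the difference in the sedation and memory thresholds is zero".

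The documents describe the two tasks as follows:
- **Naming.** Any name given within 5 seconds counts. "The dark circles with a value of 0 on the y-axis represent lack of a valid response", so responses fall to 0 as sedation deepens. Section 11.0 also warns that "no response due to sedation may be confounded by no response due to an inappropriately difficult stimulus" and will use control responses to drop problem pictures. Section 10.0 withdraws children who cannot name adequately, with adequate performance "defined as verbally responding to >80% of the pictures presented before falling asleep".
- **Recognition.** The child answers yes or no to 120 pictures, half of them shown during infusion. False positives are recorded, but no passage uses them to set the floor of the curve.

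**The concern.** The test asks whether memory is lost earlier than responsiveness. Subtracting two thresholds answers that only if each curve is fitted between limits that suit its own task. Three limits are in doubt:

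1. **Floors.** A 50-50 guess rate does not describe open naming, which has no guessing floor. For yes/no recognition, the floor for shown pictures is the child's rate of saying yes to pictures not encoded.
2. **Naming ceiling.** A child who names just over 80% of pictures while awake is retained, and some pictures may be too hard to name.
3. **Recognition ceiling.** No passage shows that recognition of pictures seen without drug effect is perfect.

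When true and fixed limits differ, both thresholds move, generally by different amounts, even for a drug with no amnesic effect of its own. The estimate in Objective 2 and the test of Hypothesis 1 use the same difference, so both carry the shift.

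The printed direction also needs correcting: G rises with x while naming falls, and 1 - G can run only from 0.5 to 0.

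**Working it through.** **The plan's own figure.** One-sample t-test, n = 35, mean 0.50, SD 1.0, two-sided 0.05: noncentrality 0.5 × √35 = 2.96 on 34 degrees of freedom gives power 0.8195. The stated 80% reproduces. The difficulty is the null value, not the arithmetic.

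**Inputs from the documents.** 60 shown pictures (half of 120), threshold at F = 0.5, and the plan's illustrations of sedation minus memory: 58 - 40 = +18 pictures (propofol) and 25 - 28 = -3 (sedative). Sizes are in pictures because the illustrations imply 10 seconds per picture while Sections 4.2 and 11.0 give 5.

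**Assumptions.** The documents give neither drug-free recognition h nor the false-yes rate g. For unsedated naming a they give only the 80% bound. The assumed pure sedative has:
- awake probability S(x) = exp(-ln 2 · (x/42)^6)
- naming probability a·S(x)
- recognition probability g + (h - g)·S(x)

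Both true thresholds are therefore 42, and the correct difference is 0.

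**Check.** Falling Weibull curves were fitted by maximum likelihood to these exact probabilities, with all shown pictures entering and the limits held fixed. Entries are sedation minus memory in pictures; a positive value looks like amnesia.

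| h / g | 0.5–1, a = 1 | 0.5–1, a = .95 | 0.5–1, a = .85 | 0–1, a = 1 | 0–1, a = .95 | 0–1, a = .85 |
|---|---|---|---|---|---|---|
| .95 / .10 | +6.2 | -0.8 | -13.1 | +0.7 | -2.5 | -7.9 |
| .90 / .10 | +12.8 | +5.7 | -6.5 | +3.0 | -0.2 | -5.7 |
| .80 / .10 | +23.9 | +16.9 | +4.6 | +8.3 | +5.1 | -0.3 |
| .95 / .50 | -2.6 | -9.6 | -21.9 | -22.8 | -26.0 | -31.5 |

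Example: at h = .90, g = .10, a = 1 with limits 0.5 and 1, the fitted thresholds are 35.4 for naming and 22.7 for recognition, a gap of 12.8 before rounding, although both truths are 42. A ceiling of 1 makes early misses nearly impossible, so the fit flattens and moves earlier.

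The 0-to-1 range is over these four pairs. With g = .50 the fitted memory threshold already lies past picture 60 (64.8 at h = .95), and lower h pushes it further out.

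**Sensitivity.** At a = 1, with the median varied over 30–50 and the shape over 3–10, the 0.5-to-1 shifts for the four rows are +3 to +7, +7.5 to +15, +14.5 to +30.5 and -17 to +0.5.

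**Effect on the test.** In 1000 simulated trials of 35 children with no true amnesia and limits 0.5 and 1, amnesia is declared in:
- 99.7% at a = 1, .95/.10
- 0% at a = 1, .95/.50, with 44% significant in the reverse direction

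At a = .85, .95/.10, 100% are significant in reverse. At a = .90, .90/.10, the mean is -1.0 with 6% significant in reverse, a cancellation.

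**Named pictures only.** Section 3.0 says a naming response "confirms that the stimulus was processed sufficiently to be learned and allow testing for subsequent recognition", which can be read as restricting the recognition fit to named pictures. A pure sedative then gives flat recognition at h. With limits 0.5 and 1 the memory threshold falls beyond the list if h > .75 and near the first picture if h < .75.

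**The case against.** The strongest reply is that the sizes rest on assumed h and g, on values of a near a withdrawal bound rather than an expected rate, and on a falling curve that the reader must supply. The practice test in Section 7.0 and the removal of hard pictures both push a towards 1. The wording on the recognition curve is permissive, and plotting responses at 1 and 0 with a 50% effect line (Section 3.0) suits a 0-to-1 curve at least as well. All of this stands. It is why ranges are shown, and why the claim is that zero is not in general the null value. It does not rescue the test, because 0-to-1 limits do not restore a zero null either.

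Some stronger readings are tempting but unsupported:
- **That the plan gives no reason for the 0.5.** It gives one, with a citation. The reason fits naming badly and is doubtful for yes/no recognition.
- **That the sponsor expects poor drug-free recognition.** Section 9.0's "few accurate responses during the memory task" is an example of insufficient data, and amnesia itself could produce it.
- **That the test is biased towards finding amnesia.** The sign depends on a, h and g.
- **That a 50% effect in Section 3.0 conflicts with 75% in Section 11.0.** Both correspond to F = 0.5.

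The consequence is also limited. Feasibility is primary, Section 9.0 calls a reliable difference premature to anticipate, and the sample size is set mainly by the timeline. Even so, Section 11.0 calls this the main hypothesis and gives a power figure for its test.

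**Conclusion.** The concern holds for Aim 2 and Hypothesis 1; the feasibility aim is unaffected. The printed model is wrong for naming, its limits for recognition are not justified, and its direction needs correcting. Zero is the right null if the fixed limits suit both tasks, or by cancellation, but not in general.

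Under the assumed pure sedative (a from 1 to .85, h from .95 to .80, g from .10 to .50) the artefact runs from about -22 to +24 pictures with 0.5-to-1 limits. With 0-to-1 limits it runs from about -31 to +8 over the four recognition pairs tabulated. It can therefore match the 18-picture illustration in either direction. These figures show what is possible. They do not predict this trial's bias, since a, h and g are unknown. A reader might infer that any significant Aim 2 result would be false. The documents do not support that; they leave a real effect and a limit artefact indistinguishable.

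**What to change.** Amend the Aim 2 text before analysis:

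- State that both curves fall with x and which pictures enter the recognition fit.
- Fit naming as A(1 - F(x)), with floor 0 and A estimated after problem pictures are dropped.
- Fit recognition of all shown pictures as g + (U - g)(1 - F(x)). Take g from the false-positive rate on novel pictures. Estimate U, for example pooled or as a random effect from the propofol children's early pictures.
- Keep the threshold at F = 0.5 for both curves, and estimate and test the difference on that scale.
- Use control data by picture position as a check on A and U. Picture order is the same for every child (Section 7.0), but the groups are not randomised (Section 12.2), so controls should not be the main source.

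An early window of 15 pictures, with 10 and 20 as sensitivity analyses, is one workable choice.

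**Cost.** No new data, but three more estimated limits and possibly less stable fits. That matters because Aim 1 counts children with usable parameter estimates; pooling the limits should help.

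**Performance.** Noise-free, the proposed form returns 0.0, but this is nearly circular because it is also the generating form. Simulation is more informative. Over 21 scenarios without amnesia, the mean difference was -0.3 to +1.6 pictures and amnesia was declared in 1.1–9.5% of trials against a nominal 2.5%, so some excess error remains. A true 18-picture effect was recovered as 17.6–18.0, or 16.7–16.8 if memory loss was gradual; fixed limits gave 20.5–28.2 (0.5 to 1) and 10.5–23.1 (0 to 1). Amnesia is understated if drug effect starts within the window or memory loss is gradual: a gradual 25-picture effect was recovered as about 24, 23 and 21 with windows of 10, 15 and 20.

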12.0 RESEARCH PARTICIPANT REGISTRATION AND RANDOMIZATION PROCEDURES

12.1 Research Participant Registration

Confirm eligibility as defined in the section entitled Criteria for Patient/Subject Eligibility.

Obtain informed consent, by following procedures defined in section entitled Informed Consent Procedures.

During the registration process registering individuals will be required to complete a protocol specific Eligibility Checklist.

All participants must be registered through the Protocol Participant Registration (PPR) Office at Memorial Sloan-Kettering Cancer Center. PPR is available Monday through Friday from 8:30am – 5:30pm at [contact]. The PPR fax numbers are [contact] and [contact]. Registrations can be phoned in or faxed. The completed signature page of the written consent/verbal script and a completed Eligibility Checklist must be faxed to PPR.

12.2 Randomization

This study does not require randomization.

13.0 DATA MANAGEMENT ISSUES

A Research Study Assistant (RSA) will be assigned to the study. The responsibilities of the RSA include project compliance, data collection, abstraction and entry, data reporting, regulatory monitoring, problem resolution and prioritization, and coordinating the activities of the protocol study team. The data collected for this study will be entered into a secure database. Source documentation will be available to support the computerized patient record. All data will be maintained by the RSA under the direct supervision of the principal investigator.

